4.5.1 Pharmacist training and support

Prior to service delivery, pharmacists will be prepared through a clinical training program (either through the Australasian College of Pharmacy or Pharmaceutical Society of Australia) to apply best practice standard of care. Furthermore, study specific training modules developed by the research team will be completed by pharmacists to ensure efficiency in the consultation process, patient consent, recruitment of patients, timely referral, and quality data collection.

4.5.2 Pharmacy consultation

The pharmacist will undertake a structured consultation with the patient in the community pharmacy guided by an IT program applying one of two clinical management protocols (Combined Oral Contraception and Progestogen-Only Contraception) which encompasses the recommendations from the Australian Therapeutic Guidelines. The clinical management protocol has been subject to co-design between community pharmacists and senior general practitioners with advice from a subject matter expert. This consultation is anticipated to take 10 minutes.

The intervention is provided under the NSW Health Authority allowing participating NSW pharmacists to supply medications as part of the trial. For the ACT, a discretionary licence will be approved for participating pharmacies.

The structured consultation is summarised in Box 1.

BOX 1

- Participant eligibility assessment, in which the pharmacist will assess if the patient meets the inclusion/exclusion criteria to participate in the study.
- Service offering, during which the pharmacist will explain the features of the study and will ask the patient if she/they is willing to participate.
- Electronic provision of the Patient information sheet and informed consent form.
- Patient's clinical assessment. During the assessment the pharmacist will elicit relevant clinical information, including medical conditions, medication history, in line with agreed clinical management protocols. If the patient is a usual patient of the pharmacy, their medication dispensing history may be checked on the computer record, if not the patient medications will be asked. Further information may be obtained from the patients' Electronic Health Record (EHR). Viewing a patients EHR is legally and professionally allowed by pharmacists, with patient consent.
- Clinical measurements of Blood Pressure and BMI will be documented at the initial patient consultation.
- After the clinical assessment, the pharmacist will use one of two clinical management protocols to proceed to resupply.
- Pharmacists may supply a continuation of the oral contraceptive pill (minimum 1 month, and up to 12 months' supply) provided the patient has seen a general practitioner (or other authorised prescribing health care professional in the last 2 years. Pharmacists are not permitted to initiate or change therapy.
- Non-pharmacological management may include:
 - Referral to see their medical practitioner, Family Planning or Sexual Health Clinic for maintaining regular women's health and sexual/reproductive health checks.
 - Counselling on the importance of getting regular cervical screening tests, breast checks, and STI testing done.
 - Counselling on the OCP supplied, i.e.,
 - How to take the OCP;
 - What side effects to expect when taking the OCP;
 - How to manage adverse effects from the OCP;
 - When the OCP is less effective;
 - What to do in event of a missed pill.
 - Provision of a Consumer Medicines Information sheet.
 - Provision of advice if they patient has any concerns regarding the OCP.
 - Provision of advice and referral, of there is a concern that the patient may be at risk for or could have contracted a sexually transmitted disease through unprotected sex, an/ or if the patient indicates that she has been sexually assaulted.
- The pharmacist will facilitate appropriate and timely referral, if required.
- The pharmacist will share a record of the supply with the patient's usual treating medical practitioner or medical practice (via fax, secure messaging software, provision of a letter to the patient, or any other approved secure means by NSW Health), where the patient has one, following consent by the patient.
- The pharmacist complies with the 'Management Protocols', including that the pharmacist makes a record of the consult in MedAdvisor pharmacy software, or an approved system by the Ministry of Health.
- The pharmacist must keep a clinical record for 7 years that contains:
 - sufficient information to identify the patient;
 - the date of the treatment;
 - the name of the pharmacist who undertook the consultation;
 - any information known to the pharmacist that is relevant to the patient's diagnosis or treatment (for example, information concerning the patient's medical history);
 - any clinical opinion reached by the pharmacist;
 - actions taken by the pharmacist;

- particulars of any medication supplied for the patient (such as form, strength and amount);
- notes as to information or advice given to the patient in relation to any treatment proposed by the pharmacist who is treating the patient;
- any consent given by a patient to the treatment proposed.
- Any medications will be dispensed via pharmacy dispensing software and labelled according to the legislative requirements outlined in the Poisons and Therapeutic Goods Regulation 2008.
- The pharmacist will remind the patient they will be followed up by the research team at 7 days. There will be patient reminders if no response, at days 9, 11 and 13 days, with a maximum of 5 attempts.

4.5.3 Implementation strategy

There will be follow up training and ongoing support as part of a translational/implementation strategy through the study period. Practice change facilitators will visit participating pharmacies to provide ongoing support, answer any queries, ensure quality data is being collected, and collect implementation data. The implementation component of the study will be underpinned by the Consolidated Framework for Implementation Research (CFIR), with the use of an adapted implementation model for community pharmacy. Implementation factors (barriers, causes and facilitators) and the Dougherty strategy classification systems, adapted to community pharmacy, will be used.

4.5.4 Considerations for the delivery of the intervention

Cost to patients

NSW - The cost of the consultation with patients (\$20) will be paid for by the NSW Government to pharmacies, irrespective of the outcome of the consultation. The patient will meet out of pocket expenses for any medicines or products provided.

ACT - The cost of the consultation with patients will be paid for by the patient receiving the service to pharmacies, irrespective of the outcome of the consultation. The patient will also meet out of pocket expenses for any medicines or products provided.

Legislative considerations

NSW - The legislative approval required for the trial has been developed and executed by the NSW Ministry of Health.

ACT - The ACT legislation process has been determined by the acting Chief Pharmacist in ACT. Whilst in NSW the Chief Medical Officer signs an Authority for the change, a licence application will need to be made by participating pharmacies in ACT. The discretionary licence (available via PDF) would be issued to authorise the 5 pharmacies in the ACT to participate in the trial (Appendix 29). Further details on the licensing can be found on the ACT website: https://www.health.act.gov.au/businesses/medicine-and-poisons-licences-and-permits

Professional indemnity for pharmacists

Pharmaceutical Defence Limited (PDL) is the major provider of professional indemnity and will cover pharmacists as part of their normal indemnity for delivery of this service. Guild Business will cover the liability from the perspective of the pharmacy premises.

4.6 Data sources

4.6.1 Community pharmacy data

During implementation of the intervention, information on health service delivery and program activities will be routinely captured in a case registration form by community pharmacists using the MedAdvisor application which is built into pharmacy software systems. For the purposes of evaluation and study participants (pharmacies and patients) will be assigned a unique study identification number.

The following information will be collected by the community pharmacists:

- 1. Name of patient
- 2. Age
- 3. Address
- 4. Documented weight, height, and BP on initial contact.
 - o BP and BMI will be documented at the first consultation
- 5. The name, dose, quantity, and manufacturer of the hormonal contraceptive dispensed or administered by the pharmacy
- 6. The date of dispensing
- 7. Name of prescriber
- 8. The name, address, telephone number of the pharmacist (address and phone number of the principal place of practice of the pharmacist is sufficient)

4.6.2 Participant (patients) self-reported data

Participants will be assessed at the registration visit (consultation) described above and this will include basic demographic and clinical information. Those assessed as eligible to participate in the trial will be followed up at Day 7 post registration to assess outcomes. This will include a brief survey administered by the George Institute either via SMS message or phone call with a link to a case report form using George Data Systems (GDS). Appendix 19 provides the case report form for the 7-day follow-up visit.

4.6.3 Implementation data

Practice change facilitators: The collection of the implementation data will be undertaken through visits/contacts (approximately monthly) within the resources available depending on the final number of community pharmacies participating, by practice change facilitators employed as part of the project. An openended discussion which, depending on the mode of contact, will vary between 10 to 20 minutes (see Appendix 23 for an implementation checklist to be used by practice change facilitators). Data will be collected using a pre-developed form in REDCap. Practice change facilitators will be trained by an implementation expert on models and frameworks of implementation science with an emphasis on the application of these to this specific study and the use of the checklist for data collection purposes.

Semi-structured interviews: The perspectives and experiences of community pharmacists and participants (patients) will be captured at 6 months and 10 months using semi-structured interviews undertaken by the George institute . Perspectives of other stakeholders will also be sought including general practitioners, professional bodies including the Pharmacy Guild, Pharmaceutical Society of Australia and the Royal Australian College of General Practitioners, and NSW Health administrators.

A maximum variation sampling technique will be used to select a diverse range of pharmacies and patients for interviews, taking into consideration pharmacy level factors such as geography, pharmacy size and participant level factors such as age, geography, presence of comorbid conditions, income status. It is anticipated that around 50 interviews in total will be conducted, however, the final sample size will be determined when it is considered the research team have achieved thematic saturation and few new themes are emerging from the interviews.

For participants (patients), interview questions will focus on experiences of health care and awareness and perceptions of services (Appendix 21). They will take no longer than 45 minutes. For community pharmacists and other stakeholders', questions will focus on implementation and contextual factors which may influence

program outcomes [36-39], sustainability, staff experiences and motivation to engage in the prescribing model (Appendix 26). These interviews will take up to 1 hour.

Data collection will be conducted by members of the research team who are experienced in qualitative research methods. These sessions will take place via telephone, videoconferencing (e.g., Zoom or MS teams), or face-to-face at a community pharmacy, depending on the participants' preference and feasibility and other factors at the time. All sessions will be audio-recorded and transcribed and detailed field notes recorded.

4.6.4 NSW Ministry of Health data

NSW Health will establish a public health register for the purposes of evaluating the trial. The NSW Public Health Act 2010 allows for the Minister for Health to establish public health or disease registers to follow up the care and treatment of patients; for infection control and disease outbreak investigations; disease risk factor monitoring in the population; monitoring the outcomes of population health interventions; and monitoring exposure to chemicals or environmental risk factors. The Centre for Epidemiology and Evidence establishes and manages a range of ad hoc and ongoing registers. Participants will be requested at registration to provide consent to access their data for the evaluation.

4.6.5 Medicare Benefits Schedule (MBS) and Pharmaceutical Benefits Scheme (PBS) data

Participants will be requested at registration to provide consent to access their MBS and PBS data for the evaluation. The Services Australia approved patient and information consent form (Appendix 23) will be used to seek consent. Participants will have the option of authorising Services Australia to provide their claim history for MBS, PBS or both.

As the study will be examining how the use of this service impacts consistency of oral contraception adherence, a 3-year lookback will be requested for PBS data. This will allow analysis of prescribing and dispensing habits over multiple prescribing and refill cycles and to assess discontinuation rates pre and post introduction of the service as a proxy to assessing adherence gaps.

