4.2 Study design

The study hypothesis will be tested using a cohort study design, applying mixed methods (quantitative and qualitative research) to assess clinical and economic indicators, implementation, and patient experience.

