4.4.2 Participant inclusion criteria

Eligible participants must meet all the following criteria, which are included in the clinical management protocols (Appendix 1 & 2):

- Natal, cis females (capable of pregnancy).
- Aged 18 years of age or over and up to and including aged 35 years.
- Present to community pharmacies in NSW or pharmacies in ACT to obtain a continuing supply of their previously prescribed oral contraceptive pill.
- Patient has been initiated on an oral contraceptive pill by their GP (or other authorised prescribing health care professional) primarily for the indication of contraception and has been stabilised on that pill for 2 years continuously.
- Patient is taking an approved oral contraceptive pill listed in the NSW Health Authority.
- Patient has seen their GP (or other authorised prescribing health care professional) for a review of their oral contraceptive pill in the last 2 years.

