4.9 Outcomes

Primary outcomes

Primary outcomes will be accessibility and acceptability of the service (based on self-report at 7-day follow up). This will be a composite measure based on patient self-reported data. It includes seven items adapted from existing questionnaires, including a validated questionnaire for perceived service quality in community pharmacies (two items) and studies of pharmacy prescribing for oral contraception, and other medications [1-6]. It will cover the following domains: (a) trust and confidence in health and medical advice provided, (b) convenience, (b) privacy during discussion with pharmacy, and (b) overall satisfaction. Each item is scored on a 7-point Likert scale. Each domain will be equally weighted, and an aggregated score calculated and scaled to a maximum score of 100.

Secondary outcomes

- **On time dispensing rates**: 36 months pre and 12 months post introduction of the intervention (assessed using the proportion of days covered method using PBS data) [40].
- **Primary care utilisation:** MBS records will be used to measure use of general practice services prior up to 36-months pre and 12 months post introduction of the intervention date (MBS data).
- **Safety outcomes**: Adherence rates to Clinical management protocols (assessed by practice change facilitators conducting regular pharmacy monitoring and inspection of data from the patient consultation IT system), hospitalisation for potential pill-related adverse events (e.g., thromboembolic disease) (NSW Health data), rates of STI tests undertaken (MBS pathology data) and adverse events.
- **Implementation outcomes**: Implementation outcomes will also be assessed to examine the fidelity, reach and adoption of the new service, and barriers and facilitators to implementation.

• **Economic outcomes:** Results from the economic analysis will be expressed as (1) net benefit in terms of implementation costs and cost savings arising from more efficient treatment pathways; and (2) cost-consequence results accounting for patient experience measures, relevant safety outcomes and implementation measures. This will be assessed using multiple data sources including MBS records for 36 months pre and 12 months post introduction of the intervention.

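### The before/after comparison of pill discontinuation in 4.6.5 is biased, by default towards an apparent rise, because eligibility selects women on past continuity

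*Protocol*

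**What the plan says.** Three parts of the protocol bear on this.

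- **Eligibility (4.4.2).** A woman must present "to obtain a continuing supply of their previously prescribed oral contraceptive pill" and must be someone who "has been stabilised on that pill for 2 years continuously".
- **Purpose of the PBS data (4.6.5).** To see how the service affects consistency of pill use, "a 3-year lookback will be requested for PBS data". One stated use is "to assess discontinuation rates pre and post introduction of the service as a proxy to assessing adherence gaps".
- **Listed secondary outcome (4.9).** On-time dispensing is compared over "36 months pre and 12 months post introduction of the intervention (assessed using the proportion of days covered method using PBS data").

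On design, 4.2 says "The study hypothesis will be tested using a cohort study design" and names no comparison group. The regression models in 4.10.1 adjust for age, comorbidity count, primary care use in the previous 3 years and SEIFA.

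Two features of the consultation (4.5.2) also matter. Supply may be "minimum 1 month, and up to 12 months" at a time. For a regular customer of the pharmacy, "their medication dispensing history may be checked on the computer record, if not the patient medications will be asked".

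**The concern.** The periods before and after registration are not selected in the same way. To enter, a woman must still be using the pill and must have used it without a break for 2 years. After registration she is free to stop. The earlier period is thus chosen partly on the outcome being compared, and the later one is not. None of the listed covariates measures past persistence, and every enrolled woman has passed the same filter, so adjustment cannot remove the difference.

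Section 4.6.5 offers this contrast as evidence of how the service affects adherence, and section 3.1 says the trial is meant to inform the future role of community pharmacists. A rise in stopping produced by the entry rule could be read as harm from the service, and a real benefit could be hidden.

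**Working it through.** The protocol states no discontinuation rate, adherence target or sample size, so there is no figure to reproduce. The check asks what the contrast shows when the service does nothing.

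**From the protocol:** 36 months before and 12 months after; 24 continuous months on the pill at entry; current use at entry; supplies of 1 to 12 months. Share of the lookback under the continuity rule: 24/36 = 67%.

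**Assumed (not in the protocol):** annual stopping risk q of 10%, 20% or 40%; monthly restart probability 0.2; 0%, 25% or 100% of current users with an earlier gap enrolled despite the rule; 0%, 50% or 90% of women given a 12-month supply that is fully recorded.

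**Permanent stopping.** Every enrolled woman is a current user, so none can have stopped for good in any of the 36 months. This follows from presenting for continued supply, even if the 2-year rule is loosely checked. If nobody ever restarted, the comparison would be 0 before against 10%, 20% or 40% in the 12 months after.

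**Stopping with restarts.** A two-state monthly model (on pill, in gap) was simulated for 400,000 women.

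- Monthly stopping probability h = 1 − (1 − q)^(1/12), which is 0.0087, 0.0184 and 0.0417.
- Rate after registration ≈ 12h, about 0.105, 0.221 and 0.500 per person-year on the pill. The simulation gives 0.105, 0.222 and 0.499.
- Rate in the last 24 months before registration: 0, by the rule.
- Rate in months −36 to −24: 0.073, 0.155 and 0.356. These are not zero, because a woman could stop then if she had restarted in time to complete 24 continuous months.
- Rate over all 36 months = (rate in the earliest year × coverage in that year) / (3 × coverage over 36 months). At 10%: 0.073 × 0.971 / (3 × 0.990) = 0.024. The other two are 0.049 and 0.108.

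| Annual risk | Before (36 mo) | After (12 mo) | Ratio |
|---|---|---|---|
| 10% | 0.024 | 0.105 | 4.4 |
| 20% | 0.049 | 0.222 | 4.5 |
| 40% | 0.108 | 0.499 | 4.6 |

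Solving the same chain exactly gives the same ratios.

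**What moves the result** (20% annual risk; differences of 0.001 are simulation noise):

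| Scenario | Before | After | Ratio |
|---|---|---|---|
| 25% of users with earlier gaps enrolled | 0.095 | 0.220 | 2.3 |
| All users with earlier gaps enrolled | 0.191 | 0.221 | 1.16 |
| Strict rule, 50% given a recorded 12-month supply | 0.049 | 0.110 | 2.2 |
| Strict rule, 90% given a recorded 12-month supply | 0.050 | 0.021 | 0.42 |
| Strict rule, true 70% reduction in stopping | 0.050 | 0.066 | 1.3 |
| 25% enrolled with gaps, true 70% reduction | 0.095 | 0.067 | 0.71 |

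In the fifth row the true rate ratio is 0.30 and the contrast shows 1.3.

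**Days covered (4.9), no service effect, 20% risk.** Strict rule: 0.980 before and 0.939 after, a fall of 4.1 points. All users with earlier gaps enrolled: 0.926 and 0.939, a rise of 1.3 points. Strict rule with 90% given 12-month supplies: 0.980 and 0.994. At 10% and 40% risk under the strict rule, the falls are 1.9 points (0.990 to 0.971) and 8.6 points (0.957 to 0.871).

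**The case against.** A reader might infer that stopping before registration is close to zero by construction and that the service must therefore appear to increase it. The documents do not support that.

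- The lookback is 36 months and the rule covers 24. Temporary gaps can appear in the remaining 12.
- Continuity may rest on what the woman says, and no check against PBS records at entry is described. The exclusion list (4.4.3) and the aim (3.2.1) do not repeat the 2-year rule, so women with recorded gaps may well be enrolled.
- A single 12-month supply could span the whole later period and hide stopping in dispensing data. A large true benefit with looser enrolment could also show as a fall.
- Sections 4.6.5 and 4.9 speak of the introduction of the service, whereas 4.7.5 uses each participant's registration date for hospital data. If the anchor were a calendar date, part of a late registrant's conditioned 24 months would fall in the later period.
- Discontinuation is not itself a named outcome in 4.9. Gap definitions are normally left to the analysis plan, which is not at hand.

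All of this stands against the absolute claim; none of it rescues the contrast. Loose enforcement dilutes the bias only to the extent that the inclusion criterion is not applied. Long supplies add a second artefact in the opposite direction. A better gap definition would not undo the selection, because the entry rule and the comparison are both fixed in the protocol.

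**Conclusion.** The point holds in this form. Entry requires current use and 2 continuous years on the pill, which conditions 24 of the 36 earlier months and none of the 12 later ones. The uncontrolled contrast of discontinuation is therefore biased, by default towards an apparent rise, and cannot be attributed to the service.

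The size is uncertain. It rests on assumed stopping and restart rates, on how strictly continuity is checked and on supply length. The spurious ratio is about 4.4 to 4.6 under strict eligibility without 12-month supplies, about 1.15 if all current users with earlier gaps are enrolled, and below 1 if most women receive a recorded 12-month supply. Days covered is affected less, and its direction is not forced.

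Severity is moderate. This concerns a secondary analysis; the primary outcome, the 7-day patient-reported composite, is untouched.

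**What to change.** **In 4.6.5:** drop the before/after contrast of discontinuation as evidence of the service's effect. Report discontinuation after registration as a 12-month cumulative incidence with 95% CI, censored at the end of available data and allowing for the length of supply dispensed. The quantity and date of dispensing are already collected under 4.6.1.

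**In 4.9:** limit the before/after on-time dispensing contrast to refill timeliness between consecutive supplies while the woman is still on the pill. Anchor it at each woman's registration date, and state that the earlier period is selected for continuous users.

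**Cost:** a few sentences and a changed analysis of data already requested. No eligibility or clinical rule changes. The loss is a before/after discontinuation figure, which could not have been interpreted as an effect of the service.
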